2.6 Handling of Screening Failures and Drop-outs

Screen failures are patients who have signed the informed consent form but fail to meet eligibility criteria for enrolment, e.g., they do not meet one or more of the inclusion criteria or do meet one or more of the exclusion criteria. Such patients will be replaced.

Patients will be informed that they have the right to withdraw from the study at any time. The investigator must determine whether voluntary withdrawal is due to safety concerns. All patients who withdraw from the study after implantation and before completing the follow-up visits per protocol will be considered as drop-outs. Patients who drop out or are withdrawn after implantation will not be replaced.

Reasons for withdrawal are:

- The patient withdraws informed consent,
- it is determined during surgery that the patient is not feasible for ARGOS-IO pressure sensor implantation,
- the ARGOS-IO pressure sensor must be removed or replaced for any reason,
- patient becomes pregnant between screening and surgery.

Unless the patient revokes his/her permission to use it, any data collected up to the point of the patient's withdrawal will be included in the safety analysis. The data of all patients who undergo implantation of the ARGOS-IO pressure sensor will be included in the efficacy analysis under the Full Analysis Set.

2.7 Randomization

No randomization will be performed.

2.8 Blinding

No blinding/masking procedures will be performed.

To avoid bias resulting from prior knowledge of the IOP value from the ARGOS-IO system on the measurement obtained with GAT, GAT will be used first.

2.9 Sample Size Calculation

The primary aim of this study is to show “safety”, which will be evaluated based on the percentage of subjects who experience an SADE (= “non-safety), as defined in the primary endpoints.. To minimize the required sample size and consequently the number of patients exposed to risk while at the same time maximizing the chances of detecting safety events, the sample size calculation follows the principle of a two-stage design as proposed by Simon (Simon, 1989). The event of interest was defined as patients with at least one serious device related adverse event (SADE) in the 3 month period immediately following implantation. Based on a probability of non-events of $p_0=0.75$ for the first stage and an overall acceptable probability of $p_1=0.94$, a sample size of at least 11 evaluable patients in the first stage and additional 11 patients in the second stage are required. This maintains a type 1 error probability of 5% and the power of 80% based on minimizing the maximal sample size. Table 2 summarizes the consequences of the sample size calculation on the study design.

Table 2: Two-stage study design

	First Stage	Overall
SADE-free Patients		
Proportion	$p_0 = 0.75$	$p_1 = 0.94$
Minimum number required	10	20
Patients with SADE		
Proportion	$1 - p_0 = 0.25$	$1 - p_1 = 0.06$
Maximum number allowed	1	2
Total Number of Patients	11	22

2.10 Planned Interim Analysis

All 22 patients will be enrolled consecutively, until a serious adverse device effect (SADE) occurs. In that case, the DSMB will be called, and decides whether the enrollment can be continued or not.

An interim analysis will be performed after half of the study population (11-14 subjects) is enrolled with a minimum follow-up of 1 month (Visit 5). Another interim analysis to assess Safety and Performance will be performed, when all patients have completed the 3 month follow-up visit, the 6 month follow-up visit and every time an SADE occurs.

In order to take the principle of the two-stage design described by Simon into account, the trial will be terminated for futility if more than 1 patient out of the first 11 patients enrolled experience at least one SADE during the first 3 months of the post-surgical follow-up period.

The study will also be stopped if the DSMB otherwise determines that severe safety risks to the patients exist.

2.11 Handling of Changes to Study Protocol

All changes of study protocol will be documented by amendments. If an amendment implies changes in the SAP, the SAP will be adapted and the adaptation will be documented in the document history.

3. Technical Aspects and Coding Conventions

All programmes will be written using SAS version 9.3 or higher. For the final analysis, tables, figures and listings will be provided in separate documents with own table of contents. For the interim analyses the separation is not mandatory. A minimum font size of 8 points will be used for the tables and figures, corresponding to a linesize of 140 digits and a pagesize of 52 lines for an output in DIN A4 format. For listings, a standard font size of 8 points with the linesize and pagesize as defined above will be used to produce the output in DIN A4 format.

The default summary statistics for quantitative variables will be the number of observations (n), mean, standard deviation (SD), median, minimum (min) and maximum (max) for those patients with data available. Additionally, the 1st and the 3rd quartiles (Q1 and Q3, respectively) may be calculated in some cases.

All summary statistics will be presented to one decimal place more than the raw value, except for the minimum and maximum values that will be presented with the same decimal precision as the raw value. Percentage values are to be presented to one decimal place.

Percentages will be presented with two decimal places. For the calculation, The number of all patients in a specified population or treatment group is used as denominator. The denominator will be specified in a footnote to the tables for clarification if necessary.

For qualitative variables (i.e. categorical data), the number (n) and percentage (%) of patients with non-missing data per category will be the default summary presentation, and where appropriate and present, the number of missing values as a “Missing” category.

Content of free-text fields will only be provided in listings but not in tables.

If the eCRF is changed by deletion of existing items, by addition of new items or by change of the response options for an item, this information will be given in the footer of the table along with the number of subjects affected by the change of the eCRF.

Courier New will be used as font for all tables, figures and listings. In headings and titles only the first word will be capitalised. Missing data will be represented on patient listings as blank field or “.”. Listings will be sorted by subject number unless specified otherwise.

3.1 Date Coding and Day Numbering

The format for presentation of date variables will be DDMMYYYY. The format for presentation of time variables will be hh.mm.

If dates are partially given, they will be completed, if necessary for the calculation of durations, according to a worst-case imputation. Deviations will be documented and explained.

All assessment dates will be related to the surgery visit. The surgery day is defined as day 0 (D0) and denoted by V01. The screening visit, which may be up to 28 days prior to surgery (Day -28 to 0) is abbreviated as SC. The 10 follow-up visits (V02-V11) are denoted as follows in Table 3:

Table 3: Time Windows

Visit name:	SC	V01	V02	V03	V04	V05	V06	V07	V08	V09	V10	V11
Indicative Days:	Up to 28 days before surgery	D0	D1	D3	D10 +/- 1 Day	D30 +/- 5 Days	D60 +/- 5 Days	D90 +/- 10 Days	D120 +/- 10 Days	D180 +/- 10 Days	D240 +/- 10 Days	D360 +/- 10 Days

3.2 Coding Systems and Conventions

3.2.1 Separation of Medical History from Concomitant Diseases

Separation of medical history from concomitant diseases will be done according to the stop date of the finding in comparison to implantation date. Each finding will be allocated unambiguously either to medical history or to concomitant diseases.

- **Medical history:** If the stop date is before implantation of the ARGOS-IO pressure sensor, the medical condition is allocated to medical history.
- **Concomitant diseases:** If the stop date is at or after implantation of the ARGOS-IO pressure sensor, the medical condition is allocated to concomitant diseases. Furthermore, if the stop date is missing or partially given and not unambiguously before start of

treatment, the worst case is assumed. Consequently, the medical condition is allocated to concomitant diseases.

3.2.2 Separation of Previous from Concomitant Medication

Separation of previous from concomitant medication will be done according to the start and stop date of medication in comparison to implantation date. Each medication will be allocated unambiguously either to previous or to concomitant medication.

- **Previous medication:** If the stop date is before implantation of the ARGOS-IO pressure sensor, the medication is allocated to previous medication.
- **Concomitant medication:** If the stop date is at or after implantation of the ARGOS-IO pressure sensor, the medication is allocated to concomitant medication. Furthermore, if the stop date is missing or partially given and not unambiguously before start of treatment, the worst case is assumed. Consequently, the therapy is allocated to concomitant medication.

3.2.3 Coding of Adverse Events and Medical History

Adverse event and medical history terms are assigned to a lowest level term (LLT) and a preferred term (PT). Furthermore, they will be classified by high level term (HLT), high level group term (HLGT) and system organ class (SOC) according to the Medical Dictionary for Regulatory Activities version in effect at the time the database is closed.

3.2.4 Coding of Medications

Previous and concomitant medications will be given based on different Anatomical Therapeutic Chemical Classification [ATC] code levels as well as by generic name.

4. Analysis Populations and Subgroups

4.1 Analysis Populations

Within the framework of this study, the following two main populations are analysed:

- **Safety Population:** consists of all patients with attempted implantation of the ARGOS-IO implant, whether or not successful.
- **Full Analysis Set (FAS):** The FAS population comprises all subjects in whom an ARGOS-IO pressure sensor was successfully implanted. Measurements recorded by the patient will not

be included into the evaluation of the FAS population. Additional information about the drop-outs: all patients who revoke their consent and agreement preoperatively will be regarded as screen failures and will not be included in the statistical evaluation. All patients who revoke their consent and agreement postoperatively will be considered withdrawals and their data will be evaluated in the safety analysis.

4.2 Subgroups

In order to investigate the impact of certain characteristics on performance, the co-primary endpoints will also be examined by the following variables in the final analysis if meaningful:

- Gender (Male/Female)
- Post-surgery complications (Yes/no)
- Successful implantation (Yes/No)
- Age groups (<67 years/≥67 years)
- Concomitant medication (Yes/No)
- Pre-treatment (Yes/No)
- Size of ARGOS-IO implant (11.3 mm/11.7 mm/12.1 mm)
- Country of investigational site
- Educational level (Primary/Intermediate/A-Level/University/Vocational/Other).

A subgroup analysis will not be performed for a subgroup, if the subgroup is too small to provide meaningful results. For example, this is the case if all subjects are in the same subgroup.

5. Data Handling

5.1 Handling of Missing Data

All data of the patients will be used as available. All analyses will be performed on observed cases only. Missing data will not be replaced. Implausible values will be only excluded from the analysis if reasonable. The reason for exclusion will be given in the footer of the table or description of the figure.

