In a recently completed early feasibility study (ARGOS-01), six glaucoma patients (4 POAG and 2 NPG) at a single university eye clinic in Germany had an earlier version of the ARGOS-IO pressure sensors implanted in the ciliary sulcus concomitantly to cataract surgery. Promising concurrence was seen between IOP profiles obtained with ARGOS-IO, GAT and DCT over the 12 months follow-up period and the ARGOS-IO system was easily used by the patients in the home setting. However, after two fibrin reactions classified as procedure-related SAEs were observed, as were multiple adverse events possibly caused by the size and/or form of the implant, the sponsor stopped the study to investigate the cause.

Analysis of an extensive databank of eye MRIs, obtained from MRI Research Inc., a company supported by the American National Institute of Health National Eye Institute, demonstrated that the ciliary sulcus undergoes a distortion in the first months following cataract extraction. This distortion, which is extenuated by the use of single piece IOLs such as those received by all patients in the ARGOS-01 study, caused a radial force to be exerted on the ARGOS-IO pressure sensor. In vitro testing was then conducted using a tool specially designed to mimic such pressure in a controlled manner. It was determined that when exposed to such force, the original ARGOS-IO pressure sensor prototype produces aberrant pressure readings and develops a curvature in its horizontal plane.

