9.12 Exclusion of particular information from the testing of the hypothesis

No particular information is planned for exclusion from the analysis.

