7.6.3	Ophthalmic examinations	24
8.	Special Statistical/Analytical Issues	25
8.1	Interim Analysis	25
8.2	Changes in the Planned Analysis	26
A.	APPENDICES	28
	List of Tables	28
	List of Figures	30
	List of Listings	31

List of Abbreviations and Key Terms

α	Type I error
ADE	Adverse Device Effect
AE	Adverse Event
ASIC	Application specific integrated circuit
ATC	Anatomical Therapeutic Chemical Classification
β	Type II error
CIP	Clinical Investigation Plan
DSMB	Data Safety Monitoring Board
FAS	Full-analysis-set
GAT	Goldmann Applanation Tonometry
HLT	High level term
HLGT	High level group term
IO	Intraocular
IOL	Intraocular lens
IOP	Intraocular Pressure
ITT	Intention to treat
LLT	Lowest level term
N	Sample number
OCT	Ophthalmic Coherence Tomography
p0	Proportion of patients in stage 1 with positive outcome
p1	Proportion of patients overall with positive outcome
POAG	Primary open angle glaucoma
PT	Preferred term
SADE	Serious Adverse Device Effect
SAE	Serious Adverse Event
SAP	Statistical Analysis Plan
SES	Safety evaluation set
SOC	System organ class
V	Visit

1. Introduction

This Statistical Analysis Plan (SAP) contains a more technical and detailed elaboration of the principal features of the statistical analyses described in the Clinical Investigation Plan Rev. G, date 05th January 2016, and includes planned detailed procedures for executing the statistical analysis of the primary and secondary variables and other data. The SAP is finalised and signed prior to hard lock of the database.

2. Study Design and Objectives

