8.2 Changes in the Planned Analysis

Departing from the planned analysis, the first DSMB meeting was conducted after 6 patients had completed Visit 4. The sponsor of this trial was enlightened that it is necessary to increase the overall sample size if this first DSMB meeting corresponds to a prepond analysis of the first stage of Simon's two stage design in order to maintain the type I and type II error. The report provided for this DSMB meeting comprised the listings and tables in the DSMB charter plus a table summarizing the compliance of subjects.

The second DSMB meeting was conducted after 11 patients completed Visit 5 (one month after implantation of the medical device). The report provided for this DSMB meeting comprised the listings and tables in the DSMB charter minus the summary of anterior segment examination results, posterior examination results, GAT measurements and ARGOS-IO measurements.

The first interim analysis independent from the DSMB was conducted after 21 subjects completed Visit 5 (one month after implantation of the medical device). The report provided comprised the listings and tables in the DSMB charter plus:

- Summaries of visual field and visual acuity results at screening and follow-up visits
- More detailed information about medical history, concomitant illnesses and previous/concomitant medications
- More detailed information about adverse events
- Additional summaries of GAT measurements and ARGOS-IO measurements including limits of agreement per visit and for all visits

The limits of agreement were provided in a separate document with corresponding table and figures. If multiple ARGOS-IO system measurements have been made at time points for which paired GAT/ARGOS-IO system measurements were to be compared, the mean of the replicate ARGOS-IO system measurements were used for agreement evaluation. Subsequently, this analysis was repeated by using the first replicate ARGOS-IO system measurement instead of the mean of the replicate measurements.

The second interim analysis independent from the DSMB was conducted after all subjects completed Visit 9 (6 months after implantation of the medical device). The report provided comprised the same tables and listings as the report for the interim analysis conducted after 21 subject completed Visit 5.

A. APPENDICES

List of Tables

Table 1	Disposition of patients (SES, FAS)
Table 2	Patient recruitment by month and by site
Table 3	Premature terminations

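### SAP 5.1 lets implausible readings be dropped from the co-primary limits of agreement on undefined judgement, with no all-values analysis required, after agreement results had been produced

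*SAP*

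**What the plan says.** SAP 5.1 begins by committing to available data and observed cases, without imputation. It then adds: "Implausible values will be only excluded from the analysis if reasonable". The only condition attached is disclosure: "The reason for exclusion will be given in the footer of the table or description of the figure". It gives no numeric range, technical criterion, responsible person or deadline, and it does not require limits with and without the excluded values. SAP 7.3 (primary limits of agreement, V05 to V09) and SAP 7.5.1 (V10 to V11) contain no exemption.

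The protocol treats wrong sensor readings as a device risk. Section 5.3 reports that, under radial force, "the original ARGOS-IO pressure sensor prototype produces aberrant pressure readings", and that the redesign is expected to reduce the pressure drift seen in the earlier feasibility study. Section 6.3 makes evaluating accuracy, precision and drift in humans a main objective of the trial.

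On timing, SAP 8.2 says the first interim analysis independent of the DSMB, after 21 subjects had completed V05, included: "Additional summaries of GAT measurements and ARGOS-IO measurements including limits of agreement per visit and for all visits". It continues: "The second interim analysis independent from the DSMB was conducted after all subjects completed Visit 9", with the same tables and listings as before. The SAP introduction says: "The SAP is finalised and signed prior to hard lock of the database". SAP 2.8 confirms that nothing is masked.

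**The concern.** In most trials an implausible laboratory or vital-sign value is noise to be cleaned. Here the measurement device is the object of study, so a wild ARGOS-IO reading that is not a recording error is an outcome. The limits of agreement are meant to contain 95% of value pairs. They carry no hypothesis test (SAP 5.3) and no acceptance limit, so the reported limits are the whole co-primary performance result.

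The criterion is undefined, so each exclusion remains a case-by-case decision up to the final analysis. It would be taken by people who can see which method gave each value and who may already know the agreement results. A footnote discloses the exclusion but leaves the narrower limits as the reported result.

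**Working it through.** **No plan figure to reproduce.** The documents state no sample size, precision target or acceptance limit for agreement. The stated sample-size figures belong to the safety design and do not bear on this point.

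**Number of pairs.** Protocol 8.7.4 schedules 4 series at V05, V07 and V09 and 2 at V06 and V08. That is 4 + 2 + 4 + 2 + 4 = 16 pairs per patient, and 16 × 22 = 352 pairs at most. Two per cent of 352 is about 7 pairs.

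**Assumptions.** The documents give no SD of GAT/ARGOS-IO differences, no error rate and no error size. Protocol 3.3.3 puts the imprecision of repeated IOP measurement at ±5 mmHg. SDs of 2.5 to 5 mmHg and offsets of 10 to 20 mmHg are assumed around that.

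**Formula.** Let a fraction f of pairs be shifted by d, with SD s for the rest. Then:
- bias shift = f × d
- total SD = √(s² + f(1 − f)d²)
- limits = mean ± 1.96 × total SD
- narrowing after removal = 1 − s / total SD

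This pools all pairs and ignores clustering within patient, which is enough to show the order of size.

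**Whole pair wrong, 7 of 352 pairs (f = 0.0199).** Width is upper minus lower limit, in mmHg.

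| Assumed SD | Width without the 7 | Width with all, d = 10 | d = 15 | d = 20 |
|---|---|---|---|---|
| 2.5 | 9.8 | 11.2 (13% narrower after removal) | 12.8 (23%) | 14.7 (33%) |
| 3.5 | 13.7 | 14.8 (7%) | 16.0 (14%) | 17.6 (22%) |
| 5 | 19.6 | 20.3 (4%) | 21.2 (8%) | 22.4 (13%) |

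**One replicate wrong.** SAP 7.3 averages the replicate ARGOS-IO readings, scheduled as three per series, so one replicate 15 mmHg off moves the pair by 15 / 3 = 5.
- SD 3, f = 0.02, one replicate wrong (d = 5): √(9 + 0.0196 × 25) = 3.08, so limits are ±6.04 against ±5.88, about 3% narrower after removal.
- SD 3, f = 0.02, all three wrong (d = 15): √(9 + 0.0196 × 225) = 3.66, so limits are ±7.18 against ±5.88, about 18% narrower.
- SD 5, f = 0.02, one replicate wrong: √(25 + 0.0196 × 25) = 5.05, about 1% narrower.

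**Other patterns, whole pairs wrong, same SD and offset ranges.** One aberrant pair changes the width by 1% to 8%. Eighteen pairs (5%) change it by 8% to 51%. One patient with all 16 pairs off changes it by 8% to 49%.

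**Bias.** The direction is not fixed. If 2% of pairs read 15 mmHg high around a true bias of zero, the bias with all data is 0.02 × 15 = +0.3, and removal returns it to zero. If the true bias is +3 and 2% read 15 mmHg low, the bias with all data is 3 − 0.3 = +2.7, and removal moves it to +3.0, away from zero.

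**The case against.** The sentence is worded as a restriction, and it follows a commitment to use all available data. Exclusions would be visible: reasons must be printed, Listings 26 and 27 give the ARGOS-IO and GAT measurements, and device deficiencies are tabulated separately (SAP 7.5.2). Protocol 10.3 requires questionable values to be queried and resolved before any analysis. The rule also covers implausible GAT values, which are not device performance. All of this stands, but none of it supplies a criterion or puts all-values limits beside the reported ones. Protocol 10.3 governs data cleaning, and a value still implausible after query is more likely to be a genuine reading.

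Four stronger readings are tempting, and the documents do not support them.

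- A reader might infer a contradiction with Protocol 9.12: "No particular information is planned for exclusion from the analysis". That section concerns testing of the hypothesis, and the tested hypothesis is the SADE rate. Protocol 9.10, headed to include spurious data, leaves data handling to the SAP. The SAP also cites a later protocol revision (G) than the one supplied (C with an addendum).
- A reader might infer that exclusion always moves the bias towards zero and favours the device. The second bias example shows otherwise. Protocol 6.3 reports ARGOS-IO values consistently above GAT in the earlier study, and Protocol 5.1.2 reports downward drift in two rabbit implants.
- A reader might infer that the trial could not show whether the redesign cured aberrant readings. The listings and footnotes would let a reader find dropped values and recompute.
- A reader might infer that values were dropped, or that the rule was written after the results were seen. SAP 8.2 does not say whether the interim limits excluded anything, and the age of the sentence cannot be established. Limits at the V09 interim are inferred from the statement that its report matched the earlier one, whose limits were supplied in a separate document.

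**Conclusion.** The point holds as a weakness in the analysis rule. SAP 5.1 gives open discretion over data that form the co-primary performance result, in an unmasked trial where agreement results had been produced at least once and very probably twice. For gross outliers, removal narrows the limits. With 2% of pairs affected, the worked cases run from about 3% (one replicate wrong, SD 3) to 33% (whole pair 20 mmHg off, SD 2.5), and less where the SD is larger or a single replicate or pair is involved. These sizes rest entirely on assumed SDs, error rates and offsets. The change in bias has no fixed direction. Since no acceptance limit exists, exclusion cannot turn a failure into a pass. What is at stake is how wide the reported disagreement appears. The change should be made before hard lock.

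**What to change.** For IOP data, replace the sentence in SAP 5.1 and cross-refer from 7.3 and 7.5.1. Suggested wording:

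*The primary and secondary limits of agreement use every recorded GAT/ARGOS-IO pair. A value is removed only if source data show a transcription error or a documented technical failure, identified without reference to the paired difference. Any other exclusion, of ARGOS-IO or GAT values, is shown only as a sensitivity analysis beside the all-pairs limits, listing the number, patient, visit and measurement method of each excluded value.*

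The cost is this wording and one added table. The downside is that the headline limits may be wider, and an odd GAT value that cannot be traced to an error stays in the primary result. The sensitivity analysis shows how much that matters.
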